10.1 Statistical Plan

Summary statistics will be produced (e.g. mean, standard deviation). Paired t test will be used to compare slit lamp biomicroscopy, lens fit and subjective scores between study lens types. Repeated Measures Analysis of Variance (ANOVA) or paired analysis will be used to compare the variables between study visits. The critical alpha level for statistical significance will be set at $p \leq 0.05$, with adjustment for multiple comparisons.

All participants who were evaluated will be used in the analysis. In the event of missing data, individual data points will be excluded in the analysis and not extrapolated from the collected data.

11 Data Quality Assurance

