CooperVision™

Study Implementation document: Protocol

CLINICAL EVALUATION OF BIOFINITY MULTIFOCAL TORIC CONTACT LENSES

Sponsor Study Code: CV-18-11
Version Number: 1.0
Implementation document Date: 21 Feb 2018
Sponsor Company: CooperVision, Inc.
Document Type: Protocol
Study Category: [REDACTED]
Clinical Sites: [REDACTED]
Site Protocol Number: C17-634

Study Sponsor Representative: _____ **Date:** _____
[REDACTED]

CooperVision Sponsor Management: _____ **Date:** _____
[REDACTED]

Site Principal Investigator: _____ **Date:** _____
[REDACTED]
[REDACTED]

Confidential

TABLE OF CONTENTS

1	Introduction	5
2	Study Objective	5
2.1	Study Hypothesis.....	5
3	Study Design	5
4	Ethics Review / Statement of Compliance	6
4.1	Relevant Standards / Guidelines.....	6
4.2	Institutional Review Board.....	6
4.3	Informed Consent	6
5	Clinical Trial Registration	7
6	Potential Risks and Benefits to Human Subjects	7
7	Materials and Methods	8
7.1	Subjects	8
7.2	Study Materials	9
7.3	Visit Schedule and Procedures	11
8	Adverse Event Reporting	16
8.1	Adverse Event Definitions	16
8.2	Procedures for Adverse Events.....	18
8.3	Reporting Adverse Events.....	18
8.4	Discontinuation from the Study	19
9	Device Malfunctions	19
10	Statistical Analysis	20
10.1	Statistical Plan	20
11	Data Quality Assurance	20
11.1	Study monitoring.....	20
11.2	Record keeping.....	21
11.3	Record retention	21
11.4	Data Entry / Data Management.....	21
11.5	Confidentiality	22
11.6	Publication	22
12	Study Costs	22

DOCUMENT CHANGE HISTORY

Version	Originator	Description of Change(s)	Date
1.0	[name]	Original Protocol	21 February 2018

1 Introduction

CooperVision, (CVI) is extending the power range of the commercially available Biofinity silicone hydrogel contact lenses to include multifocal toric silicone hydrogel contact lenses (Biofinity MFT).

This study is to evaluate the clinical performance of the Biofinity MFT lenses.

2 Study Objective

The objective of this non-dispensing clinical study is to compare the clinical performance of Biofinity Multifocal Toric (BF MFT) with Proclear Multifocal Toric (PC MFT) contact lenses.

The primary variable of interest is:

- Visual acuity (VA)

The secondary variable of interest is:

- Subjective assessments of visual performance

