2.1 Study Hypothesis

The study hypothesis is that the Biofinity Multifocal Toric lenses will not be clinically inferior to Proclear Multifocal Toric lenses.

3 Study Design

This non-dispensing, subject masked, randomized, bilateral crossover study will compare the clinical performance of Biofinity Multifocal Toric contact lenses.

Up to 20 subjects, who have worn soft contact lenses in the last six months, will be enrolled.

This study will be composed of two parts. Part A will involve a screening/baseline visit for the determination of subject's contact lens prescription based on their spectacle refraction. With the

information obtained from Part A, Biofinity Multifocal Toric and Proclear Multifocal Toric contact lenses will be made to order on a per-patient basis for use in Part B to assess the clinical performance of the lenses.

Subjects must be able to participate in both parts of the study; Part A of the study will last approximately 1-2 hours duration and Part B will last approximately 3-4 hours duration.

4 Ethics Review / Statement of Compliance

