7.1 Subjects

Up to twenty subjects will be needed to complete the study. Each subject will be given a unique ID number. Additionally, all subjects must meet the study inclusion and exclusion criteria listed below. Potential subjects will be identified from the investigators' clinic database records and/or will be actively recruited by advertisements circulated at the investigational sites approved by the appropriate IRB.

Inclusion Criteria

A person is eligible for inclusion in the study if he/she:

- Has had a self-reported oculo-visual examination in the last two years.
- Is aged 40–75 years, inclusive and has full legal capacity to volunteer.
- Has read and understood the participant information sheet.
- Is willing and able to follow instructions and maintain the appointment schedule.
- Is able to participate in Parts A and B related to this work.
- Has a contact lens spherical prescription between +10.00 to -10.00D (inclusive).
- Has an Add component to their spectacle refraction (between +0.75 and +2.50DS).
- Has astigmatism between -0.75 and -5.75DC (based on the vertexed ocular refraction in each eye).
- Can be satisfactorily fitted with the study lenses.
- Is correctable to a visual acuity of 20/40 (0.30 logMAR) or better (in each eye) with their habitual vision correction or 20/25 (0.10 logMAR) best-corrected.
- They have successfully worn soft contact lenses in the last six months
- Has clear corneas and no active ocular disease.
- Has not worn lenses for at least 12 hours before the examination.
- Has an up-to-date pair of spectacles.

Exclusion Criteria

A person will be excluded from the study if he/she:

- Has never worn contact lenses before.
- Has any systemic disease affecting ocular health.

Confidential

- Is using any systemic or topical medications that will affect ocular health.
- Has any ocular pathology or severe insufficiency of lacrimal secretion (moderate to severe dry eyes) that would, in the opinion of the investigator, affect the wearing of contact lenses.
- Has persistent, clinically significant corneal or conjunctival staining using sodium fluorescein dye that would, in the opinion of the investigator, be problematic for their participation in the study.
- Has any clinically significant lid or conjunctival abnormalities, active neovascularization or any central corneal scars.
- Is aphakic.
- Has undergone corneal refractive surgery.
- Has a history of anaphylaxis or severe allergic reaction.

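### Section 10.1 leaves visual acuity, the primary variable, out of its between-lens test, and a difference test at p ≤ 0.05 cannot show the stated non-inferiority

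*Combined protocol and SAP*

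**What the plan says.** Section 2 sets the objective, to "compare the clinical performance of Biofinity Multifocal Toric (BF MFT) with Proclear Multifocal Toric (PC MFT) contact lenses". Under "The primary variable of interest is" it lists visual acuity alone; subjective assessment of vision is secondary. Section 2.1 gives one hypothesis: "The study hypothesis is that the Biofinity Multifocal Toric lenses will not be clinically inferior to Proclear Multifocal Toric lenses". On numbers, Section 7.1 says: "Up to twenty subjects will be needed to complete the study".

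Section 10.1 is the whole statistical plan, and it shows no redaction. It contains two comparisons:

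- between lenses: "Paired t test will be used to compare slit lamp biomicroscopy, lens fit and subjective scores between study lens types";
- between visits: "Repeated Measures Analysis of Variance (ANOVA) or paired analysis will be used to compare the variables between study visits".

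It has one criterion: "The critical alpha level for statistical significance will be set at" p ≤ 0.05, "with adjustment for multiple comparisons". Neither the adjustment method nor the family of tests is named.

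Contact-lens VA is measured under Section 7.3.3.2 at distance and near, for the right eye, the left eye and both eyes. Section 7.3.4 repeats this for the second lens pair. Table 2 ticks contact-lens VA only in the lens fitting and exit column.

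**The concern.** There are two faults, and the second stands even if the first is only loose wording.

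1. **The primary variable has no stated between-lens analysis.** The paired t test covers three named variables, and VA is not one of them. The between-visit comparison cannot fill the gap as written, because both lens types are worn in the same part of the study.
2. **The criterion does not match the hypothesis.** Non-inferiority is a claim that any deficit is smaller than a stated margin. A test of zero difference does not address that claim, and the visible text has no margin, confidence-interval rule or non-inferiority test.

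A real VA deficit with Biofinity MFT could therefore come out non-significant in a small sample and be read as not inferior. The multiplicity adjustment makes this worse: a stricter alpha makes non-significance easier to reach. And because no VA measure is designated primary, the conclusion could rest on whichever result looks best.

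**Working it through.** **Can the plan's own figure be reproduced?** No. The figure of up to 20 subjects comes with no margin, SD, effect size or power.

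**Counts from the text.** Variables named for between-lens testing: 3, none of them VA. Visible contact-lens VA measures per lens pair: 2 distances × 3 (right, left, both) = 6, none designated primary. Further text in Section 7.3.3 is redacted, so 6 is a minimum.

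**Assumptions.** The documents give no SD, so deficits are expressed in units of the SD of the within-subject difference (δ = deficit/SD). The alpha of 0.05/6 assumes a Bonferroni adjustment over the six visible measures. Tests are taken as two-sided.

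**Chance that a real deficit is non-significant.** The paired t statistic follows a noncentral t distribution with n − 1 degrees of freedom and noncentrality δ√n. For n = 20 and δ = 0.5, the noncentrality is 0.5 × 4.472 = 2.236. The critical values on 19 df are 2.093 (alpha 0.05) and 2.944 (alpha 0.05/6).

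| n | True deficit | Non-significant at 0.05 | Non-significant at 0.05/6 |
|---|---|---|---|
| 20 | 0.25 SD | 81% | 95% |
| 20 | 0.5 SD | 44% | 73% |
| 20 | 0.75 SD | 11% | 34% |
| 20 | 1.0 SD | 1% | 8% |
| 15 | 0.5 SD | 56% | 82% |

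A simulation of 200,000 trials at n = 20 and 0.5 SD gave 43.5% and 72.5%.

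**Largest observed deficit that is still non-significant, n = 20.**
- At 0.05: 2.093/4.472 = 0.468 SD.
- At 0.05/6: 2.944/4.472 = 0.658 SD.

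The half-width of the ordinary 95% confidence interval is also 0.468 SD. A result that just misses significance at 0.05 is therefore compatible with a true deficit of up to 0.468 + 0.468 = 0.94 SD.

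**The interval rule.** If non-inferiority requires the upper limit of a two-sided 95% interval to lie below the margin, a true deficit equal to the margin is wrongly accepted 2.5% of the time, whatever the SD.

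**The opposite error.** With an assumed SD of 0.05 logMAR, a deficit of 0.02 logMAR (0.4 SD) is significant at 0.05 about 40% of the time with 20 subjects, although it could lie well inside a margin.

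**Precision with 20 subjects.** The half-width is 0.468 × SD:
- SD 0.05: 0.023 logMAR;
- SD 0.10: 0.047 logMAR;
- SD 0.15: 0.070 logMAR.

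**Power of the interval rule with 20 pairs and no true difference.** The noncentrality is (margin/SD) × √20. The margins below are illustrations, not proposals.
- Margin 0.10 logMAR: 81% at SD 0.15 and 56% at SD 0.20.
- Margin 0.05 logMAR: 99% at SD 0.05, 56% at SD 0.10 and 29% at SD 0.15.

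**The case against.** The best defence is that VA, as the primary variable, is naturally one of the variables in the between-visit sentence. That sentence allows a paired analysis, and in a crossover study a paired lens comparison is what anyone would run. That is probably the intention, so the omission may be a drafting error. It still needs correcting, and it does not rescue the criterion: the comparison would remain a test of zero difference.

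It can also be said that the plan nowhere states that non-significance will be read as non-inferiority. That is true. But it offers no other route from the data to its hypothesis, so either the hypothesis goes untested or it is inferred from non-significance.

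The percentages depend on assumed effect sizes, and this is fair. Large deficits are seldom missed: at 1.0 SD, 1% at alpha 0.05. No document figure says which deficit is clinically relevant, and 0.05/6 is only one possible adjustment. The figures show scale; the argument does not rest on them.

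Parts of Section 7.3.3 are redacted, so the absence of a primary measure can be asserted only of the visible text. That text includes Sections 2 and 10.1, where such a designation would be expected. Finally, this is a short, non-dispensing study of CE-marked lenses, so the risk is an over-read conclusion rather than harm to subjects.

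**Conclusion.** The concern holds and should be fixed before any data are analysed. Followed exactly, Section 10.1 gives no between-lens analysis of the primary variable. Followed as probably intended, it gives a difference test that cannot support the Section 2.1 hypothesis at any effect size or SD. For scale, a true deficit of 0.25 to 0.75 SD is non-significant in 81% to 11% of 20-subject trials at 0.05, and in 95% to 34% at 0.05/6. These ranges rest on assumed deficits, a two-sided test and an assumed Bonferroni divisor of 6. The absence of a margin and of a primary VA measure is a statement about the visible text.

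**What to change.** Amend Section 10.1 to say the following:

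- The primary analysis is the within-subject difference in contact-lens logMAR VA at Part B, Biofinity MFT minus Proclear MFT, with a two-sided 95% confidence interval.
- It is made on one measure named in advance. The sponsor chooses it; binocular distance is one option, and near VA also deserves thought for a multifocal lens.
- Non-inferiority is concluded only if the upper limit lies below a stated logMAR margin. The sponsor sets and justifies the margin before data are seen, because the documents give none.
- A non-significant difference is not evidence of non-inferiority.
- All other VA measures are secondary.

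Limit the between-visit comparison to variables recorded at both visits; in the visible text these are VA with spectacles or habitual prescription, and slit lamp findings. Since lens order is randomised, also say whether the analysis adjusts for period.

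The change adds no visits, measurements or subjects, because the paired VA data are already scheduled. The cost is commitment: the sponsor must fix a margin and a measure in advance, and if the margin is small relative to the SD, 20 subjects or fewer may give an inconclusive result.

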7.2 Study Materials

7.2.1 Contact Lens

Subjects will be randomized to receive either the Test or Control lens as the first pair of contact lenses as per the randomization schedule. The lenses used in this study will be provided by the Sponsor.

Details of the CE marked contact lenses are shown in Table 1.

Table 1: Study lenses

	Lens 1	Lens 2
Name	Biofinity Multifocal Toric	Proclear Multifocal Toric
Manufacturer	CooperVision	CooperVision
Material	Comfilcon A	Omafilcon B
EWC (%)	48%	62%
Base Curve (mm)	8.7	8.4 / 8.8
Diameter (mm)	14.5	14.4
Spherical powers (DS)	+10.00 to -10.00 (0.50 steps after $\pm 6.50D$)	+20.00 to -20.00 (0.50 steps after $\pm 6.50D$)
Cyl Powers (DC)	-0.75 to -5.75 (0.50 steps)	-0.75 to -5.75 (0.50 steps)
Axis (°)	5 to 180 (5 degree steps)	5 to 180 (5 degree steps)
Add (D)	+1.00, +1.50, +2.00, +2.50 (D & N)	+1.00 to +4.00 (D & N)

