7.3.3.2 Visual Acuity / Lens Fitting

1. Binocular and monocular visual acuity will be assessed at distance (equivalent to 6M) and near (40cm) before over-refraction:
 - HIHC* logMAR VA (equivalent to 6M, 40cm) – (OD, OS, OU)

2. [REDACTED]

[REDACTED]

[REDACTED]

[REDACTED]

[REDACTED]

- [REDACTED]

- [REDACTED]

- [REDACTED]

[REDACTED]

[REDACTED]

- [REDACTED]

- [REDACTED]

- [REDACTED]

- [REDACTED]

7.3.3.5 Contact lenses to be removed by investigator and retained for return to the Sponsor.

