7.3.4 Lens Pair 2 and Exit

1. The second lens type will be inserted according to randomization schedule.
2. The same procedures outlined in Section 7.3.3 will be repeated.
3. Subjects to assess their preference between Lens Pair 1 and 2 for a number of considerations according to the CVI guidelines in Appendix 3 (5 point Likert scale) (Strong Pair 1, Slight Pair 1, no preference, Strong Pair 2, Slight Pair 2):
 - [REDACTED]
 - [REDACTED]
 - [REDACTED]
 - Overall Vision Preference
 - [REDACTED]
 - [REDACTED]
 - [REDACTED]
4. Contact lenses to be removed by investigator and retained for return to the Sponsor.
5. Slit lamp biomicroscopy will be assessed according to the guidelines set out in the CVI Grading scales (Appendix 1).
6. Exit high contrast logMAR visual acuity (OD, OS) with spectacles or habitual Rx in phoropter or trial frame
7. The subject will be discharged and asked to sign the exit statement.

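### The between-lens paired t test in section 10.1 leaves out the randomised lens order; a period term is a cheap gain in precision and removes a possible shift

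*Combined protocol and SAP*

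**What the plan says.** Section 3 (Study Design) sets the design: "This non-dispensing, subject masked, randomized, bilateral crossover study will compare the clinical performance" of the lenses. Section 7.2.1 says what is randomised: "Subjects will be randomized to receive either the Test or Control lens as the first pair of contact lenses". Sections 7.3.3 and 7.3.4 put both pairs in the one Part B visit. Pair 1 is inserted, assessed and removed; then "The second lens type will be inserted according to randomization schedule" and the same procedures are repeated. Acuity is among them: "Binocular and monocular visual acuity will be assessed at distance (equivalent to 6M) and near (40cm) before over-refraction".

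For the comparison of lenses, section 10.1 states that "Paired t test will be used to compare slit lamp biomicroscopy, lens fit and subjective scores between study lens types". A further sentence reads "Repeated Measures Analysis of Variance (ANOVA) or paired analysis will be used to compare the variables between study visits". Neither names period, order or sequence. On numbers, section 7.1 says "Up to twenty subjects will be needed to complete the study", and section 10.1 adds "In the event of missing data, individual data points will be excluded in the analysis and not extrapolated from the collected data". The available text contains no description of a balanced or blocked schedule and no plan to check for a period effect.

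**The concern.** Lens order is a design factor that the trial creates and records, yet the analysis ignores it. Subjects repeat the same assessments with a second pair in one session, so practice or fatigue could make Pair 2 score differently from Pair 1. The documents neither quantify such an effect nor rule it out.

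The repeated-measures sentence does not fill the gap. It compares study visits, and both lenses are worn in one visit. Visual acuity, the primary variable, is not named in the paired t test sentence, and no order-adjusted analysis is stated for it anywhere else.

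The hypothesis in section 2.1 is non-inferiority, so the width and position of the interval for the lens difference carry the conclusion. An unmodelled period effect widens that interval and, with unequal orders, moves it.

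**Working it through.** **Inputs.** From the documents: two lenses, two orders, N up to 20, alpha 0.05 (taken as two-sided). They give no SD, effect size, margin, period effect or split between orders, so there is no stated figure to reproduce. Everything below is a range over assumed values.

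**Set-up.** Let d be Biofinity minus Proclear within a subject, with SD 1, and τ its true mean. Let p be the Pair 2 minus Pair 1 effect in the same units. Let n1 subjects wear Biofinity first and n2 wear Proclear first. The mean of d is τ − p in the first group and τ + p in the second.

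- Paired t: the estimate has expectation τ + p(n2 − n1)/N, and E[s²] = 1 + 4·n1·n2·p²/(N(N − 1)), with N − 1 degrees of freedom.
- Period-adjusted: the average of the two order-specific means has expectation τ and variance (1/n1 + 1/n2)/4, with N − 2 degrees of freedom.

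**Interval width, 10/10.** Adjusted half-width: 2.101 × √(0.2/4) = 0.470, whatever p is. Paired half-width at p = 0.25: E[s²] = 1 + 400 × 0.0625/380 = 1.066, so 2.093 × √(1.066/20) = 0.483. The ratio is 1.028. The same formula gives 0.996 at p = 0, 1.0015 at p = 0.1 and 1.120 at p = 0.5.

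**Interval width, 12/8.** The adjusted half-width is 0.479, and the ratios at p = 0, 0.1, 0.25 and 0.5 are 0.976, 0.981, 1.006 and 1.092.

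**Break-even.** Adjustment narrows the interval only when p exceeds 0.085 SD at 10/10, 0.13 at 11/9, 0.22 at 12/8 and 0.475 at 14/6.

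**Shift.** Its size is p|n1 − n2|/N. At 12/8 it is 0.2p: 0.02, 0.05 and 0.10 SD for p = 0.1, 0.25 and 0.5. If a 10/10 schedule loses two usable pairs from one order, it is 2/18 = 0.11p. The adjusted estimate has no shift.

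**Power for an assumed lens difference of 0.625 SD (simulation, N = 20).**

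| p (SD) | 10/10 paired | 10/10 adjusted | 12/8 paired, shift opposes | 12/8 paired, shift reinforces | 12/8 adjusted |
|---|---|---|---|---|---|
| 0.1 | 75% | 75% | 72.5% | 78% | 74% |
| 0.25 | 73% | 75% | 66% | 80% | 74% |
| 0.5 | 67% | 75% | 51% | 81% | 74% |

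**No true lens difference.** At 10/10 the paired test is conservative: type I error is 4.9% at p = 0.1, 4.3% to 4.6% across simulation runs at p = 0.25, and 2.9% at p = 0.5. At 12/8 with p = 0.25 its total is 4.9%, but the tails are lopsided at 3.6% and 1.3%, against 2.5% each when adjusted.

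**How likely is imbalance?** The schedule is not in the available text. If it were simple 1:1 randomisation (an assumption), 20 subjects would split exactly 10/10 18% of the time and 12/8 or worse about 50% of the time.

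**The case against.** The strongest reply is that nothing here is an error. The paired t test is valid over the randomisation and conservative when orders are equal, and all the harm depends on an effect the documents never mention. Adjustment is also not free. With no period effect, power for a 0.625 SD difference falls from 75.5% to 73.6% at 12/8 and to 67.8% at 14/6. Under simple randomisation the paired test is slightly stronger on average below about 0.25 SD: 75% against 73% at p = 0.1. The schedule may well be balanced, and with both lenses worn in one visit there is little scope for loss between periods. The 66% and 51% figures need both a 12/8 split and a shift in the unfavourable direction.

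All of that stands, and it limits the weight of the point. It does not remove it. Balance abolishes the shift but not the inflated residual SD. Even a balanced schedule does not guarantee equal analysable orders, because enrolment is capped rather than fixed and missing points are dropped outcome by outcome. At equal orders the cost of adjusting is 0.3 points of power or less.

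Two limits of scope also stand. The figures suit approximately continuous outcomes recorded with each lens. They do not apply to the exit preference items, which are single comparative responses. Nor do they apply to slit-lamp grades, unless those are recorded per lens. The visible text places slit lamp before Pair 1 and after Pair 2 is removed, and parts of section 7.3.3 are redacted.

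**Conclusion.** The point holds as a worthwhile improvement, not as a finding that the planned test is invalid. Section 10.1 does not use the randomised order in the lens comparison, and no other available text supplies the adjustment. The loss is negligible for period effects below about 0.1 SD with equal orders. At 10/10 it is modest at 0.25 SD (interval 3% wider, about 2 points of power) and material at 0.5 SD (12% wider, about 8 points). Unequal analysable orders add a shift of p|n1 − n2|/N in that study's estimate, in either direction. These sizes rest on assumed period effects, N = 20, an assumed difference of 0.625 SD for power, two-sided 5% testing and approximately normal differences. Confidence is medium, because neither the period effect nor the split between orders is known.

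**What to change.** In section 10.1, state that between-lens differences for outcomes recorded with each lens will be analysed with lens, period and sequence as fixed effects and subject as a random effect. These outcomes are visual acuity, subjective scores and lens fit, with slit-lamp grades included only if taken per lens. Report Biofinity minus Proclear with its 95% CI, and the analysable number in each order for each outcome.

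Use one value per subject per lens, such as binocular acuity or the mean of the two eyes. With complete data the estimate is then the average of the two sequence-specific mean differences, with variance pooled within sequence; the two-sample form of the crossover t test gives the same result. If eye-level data are entered instead, add a random subject-by-lens term. In simulation at 10/10 with no lens difference, entering both eyes with only a random subject effect gave type I error of 9.4%, 14.9% and 21.1% at assumed between-eye correlations of 0.25, 0.5 and 0.75. This is a safeguard for the proposed model; the plan does not specify that analysis.

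The period term does not remove carryover, and the text should not claim that it does.

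The cost is two or three sentences and no new data, since lens order is known from the randomisation schedule. If there is no period effect, power for a 0.625 SD difference falls from 75.5% to 75.3% at 10/10, 74.9% at 11/9, 73.6% at 12/8 and 67.8% at 14/6.
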